Statistical Plan, Results and Conclusions for:

A Clinical Decision Support Tool for Electronic Health Records (Official Title)

NCT number 02697643

Document Date: August 9, 2018

Analytic Approach.

Primary Analytic Approach. We are interested in learning whether participants in the intervention condition, BH-CDS, as compared to the control condition, treatment as usual, have (1) greater access to wraparound services, (2) more treatment visits, and (3) longer retention in treatment. As secondary hypotheses, we will examine whether the intervention condition, as compared to the control condition, will be associated with significantly (1) greater psychosocial outcomes, and (2) reduced drug use. A mixed model analytic approach was chosen for its ability to: adjust for individual-level covariates; take into account nesting of clients within counselors; and efficiently maximize the correlated nature of the repeated measures data in the design. Each mixed model will include fixed effects (condition, time and condition-by-time); random effects (clients nested within counselors); repeated measures variation (time); as well as potential counselor-level demographic covariates (e.g., experience level) and client-level demographic covariates (i.e., age). Non-significant covariates will be removed systematically. After arriving at the final model for each analysis, the condition-by-time effect will be examined for significance. In the presence of a significant condition-by-time effect, Bonferroni corrected post-hoc contrasts will be conducted to test for differences between conditions on mean change from baseline to one month follow-up and baseline to three month follow up

Analyses by Hypothesis

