Primary Hypothesis 1: Clients in the experimental condition will have significantly greater matched evidenced-based and wraparound services than clients in the control condition. To address this hypothesis, a chart review was conducted to enumerate services received during the study period. The percentage of services that clients in the experimental condition received from the list of tailored recommendations was calculated. We then compared this percentage to the percentage of services that clients in the control condition would have received had they been in the experimental condition and received tailored recommendations. Because all clients participating in the study completed the PDE, we were able to determine which set of recommendations clients in the control condition would had received had they been in the experimental.

Primary Hypothesis 2: Clients in the experimental condition will have greater engagement in treatment than clients in the control condition. Engagement in treatment was calculated by dividing the number of treatment sessions attended during the study period by the total number of scheduled treatment sessions (i.e., opportunities for treatment), a sum of treatment sessions attended plus the number of scheduled sessions that the client did not show up for (no-show). An independent samples T-test was utilized to determine whether there were statistically significant differences between participants in the experimental and control groups with respect to treatment engagement.

Primary Hypothesis 3: Clients in the experimental condition will have less frequent use of substances than clients in the control condition. Use of substances was measured by the number of relapses during the study period. An independent samples *T*-test was conducted to evaluate whether participants number of relapses differed significantly between the experimental and control groups.

Primary Hypothesis 4: Clients in the experimental condition will have greater biopsychosocial functioning than clients in the control condition. Biopsychosocial functioning was captured by the seven ASI-MV composite scores. The ASI-MV was administered at baseline, 1-month follow-up and 3-month follow-up. Change in the ASI-MV composite scores was evaluated over time and across participant groups with a repeated measures mixed model.

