Primary Hypothesis 5: Clients in the experimental condition will have greater cost effectiveness than clients in the control condition. Costs of services provided to the participating clients in the experimental and control conditions during the study time period was estimated in the following way. Services received by each client as documented during the chart review process for Hypothesis 1 above. The cost of each service was estimated using the CPT code for that service (e.g., group psychotherapy = 90853). To establish consistent costs, estimates of cost for each CPT code were derived from Medicare reimbursement estimates in Massachusetts using online tools (e.g., https://www.findacode.com). While not precise, use of Medicare reimbursement is often used to get a general and relative sense of service costs across states. This is especially useful for comparing groups (e.g., experimental versus control), rather than attempting to generate precise cost estimates. Costs per individual were summed and averaged for t-test comparison between experimental and control groups. If patient outcomes are superior for one group, this test would determine whether the outcome difference is associated with greater or lesser costs.

Primary Hypothesis 6: Counselors in the experimental condition will report satisfaction with the BH-CDS Program. At the end of the study, participating counselors were asked to complete a satisfaction survey, which included both open-ended questions and Likert-type rating scale questions. Due to the small number of counselors in the experimental and control groups, formal statistical significance testing was not conducted. Instead, these data were analyzed descriptively. Open-ended text were subject to qualitative thematic analysis.

Results

Counselor Participants. A total of 24 counselors at four outpatient substance abuse treatment facilities around the United States participated in the current study.

Client Participants. One hundred and ninety patients completed consent forms and completed baseline surveys. Of these, 140 participants were fully enrolled into the study (completed the PDE, counselors obtained recommendations from the BHCDS system, participants completed the baseline survey). Forty-seven participants were randomized into the control, TAU, condition and 93 were randomized into the experimental condition. Demographics were relatively similar across the experimental and control conditions.

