Primary Hypothesis 1: Clients in the experimental condition will have significantly greater matched evidenced-based and wraparound services than clients in the control condition. Results test indicated no significant difference for experimental and control groups.

Primary Hypothesis 2: Clients in the experimental condition will have greater engagement in treatment than clients in the control condition. T-tests indicated that the experimental and control groups did not differ with respect to treatment engagement.

Primary Hypothesis 3: Clients in the experimental condition will have less frequent use of substances than clients in the control condition. The mean number of relapses during the study period for the experimental group was not significantly different from the control group.

Primary Hypothesis 4: Clients in the experimental condition will have greater biopsychosocial functioning than clients in the control condition. Results for psychiatric status, medical status, alcohol use, family status, or drug use were not significant. Employment status results suggest that participants in the experimental, CDS, condition had significantly fewer legal problems than controls.

Primary Hypothesis 5: Clients in the experimental condition will have greater cost effectiveness than clients in the control condition. The CDS program did not yield significantly different costs effectiveness than the control group.

Primary Hypothesis 6: Counselors in the experimental condition will report satisfaction with the BH-CDS Program. Overall, counselors found it easy to complete the CDS program and reported that their clients' reaction was "neutral" or "positive" (no counselors reported a negative client reaction).

Counselors exposed to the tailored recommendations, reported that they were easy to understand, easy to integrate into the client's treatment plan, and useful for informing treatment decisions and were more likely to incorporate the tailored recommendations into future treatment planning.

Conclusion

Although the use of clinical decision support is promising, the present effort was unable to empirically demonstrate a direct impact on outcome, retention, amount of service delivered or cost. Further research on the impact of clinical decision support for substance use treatment is warranted.

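### Two of the three stated primary questions, number of visits and retention, have no endpoint or result, yet the Conclusion speaks to retention; the Hypothesis 2 ratio measures neither directly

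*SAP*

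**What the plan says.** The Primary Analytic Approach sets three primary questions. The first is access to wraparound services; the others are "2) more treatment visits, and (3) longer retention in treatment". The same section assigns a mixed model to the analyses: "After arriving at the final model for each analysis, the condition-by-time effect will be examined for significance", followed by contrasts testing "differences between conditions on mean change from baseline to one month follow-up and baseline to three month follow up".

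Under Analyses by Hypothesis, Primary Hypothesis 2 concerns engagement, calculated by "dividing the number of treatment sessions attended during the study period by the total number of scheduled treatment sessions". The denominator is spelled out as "a sum of treatment sessions attended plus the number of scheduled sessions that the client did not show up for (no-show". The test is not the mixed model: "An independent samples T-test was utilized to determine whether there were statistically significant differences between participants in the experimental and control groups".

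In the Results, the only finding on this hypothesis is that "T-tests indicated that the experimental and control groups did not differ with respect to treatment engagement". No visit count or time in treatment is reported. The Conclusion then names retention, alongside outcome, amount of service and cost, as something on which no direct impact could be shown.

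**The concern.** A primary question should lead to a defined endpoint, an analysis and a result. Here two of the three stop at the opening paragraph, and one of those two, retention, reappears in the Conclusion. A reader will take that as a tested null finding on a primary question, when no retention analysis is reported.

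The natural defence is that engagement stands in for both. It can do so only if the Hypothesis 2 ratio moves when visits or retention move. If it does not, the reported absence of a difference shows similar attendance at scheduled sessions and leaves open whether the arms had similar numbers of visits or similar time in treatment.

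**Working it through.** **Step 1. Map questions to endpoints and results.** The SAP states no figure on this point, so there is none to reproduce.

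| Hypothesis | Endpoint defined | Visit count? | Time in treatment? |
|---|---|---|---|
| 1 | Percentage of recommended services received | No | No |
| 2 | Attended / (attended + no-show) | Numerator only | No |
| 3 | Number of relapses | No | No |
| 4 | Seven ASI-MV composites | No | No |
| 5 | Summed service cost per client | Indirectly, price-weighted | No |
| 6 | Counselor satisfaction | No | No |

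The Results cover these six and nothing else.

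**Step 2. Does the general mixed model fill the gap?** It is judged by condition-by-time and by change from baseline. A visit total over the study period, or a length of stay, gives one value per client and has no baseline value. The hypothesis sections apply the repeated-measures model only to the ASI-MV scores.

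**Step 3. What the ratio measures.** With A attended and N no-shows, ratio = A / (A + N), so visits A = ratio × scheduled sessions.

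- Scheduled volume cancels, whatever the no-show rule: 4/5 = 0.80 and 20/25 = 0.80, with five times the visits in the second case.
- Ratio and visits can point in opposite directions: 12 scheduled at 75% gives 9.0 visits; 18 at 65% gives 11.7 visits with a lower ratio.
- Response to dropout depends on the counting rule. If nothing after departure counts as a no-show, 2 attended of 2 and then leaving scores 2/2 = 1.00. If every remaining session of an equal schedule counts, the ratio is visits divided by a constant.

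**Step 4. Illustration of the consequence.** The arm sizes, 47 control and 93 experimental, come from the Results. Every other input is assumed. Each scenario uses 10,000 simulated trials, a two-sided client-level t-test at 0.05 and no counselor clustering. The simulation standard error is at most √(0.25/10,000) = 0.005.

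*(a) Schedule volume.* Scheduled sessions S = 1 + Poisson or gamma-Poisson. Control mean is 12, and control SD is √(11 + d × 11²), which is 3.3, 4.8 or 6.4 for dispersion d = 0, 0.10 or 0.25. Each client's attendance probability is Beta with mean 0.75 and concentration 8, and visits are binomial.

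| Mean scheduled, control vs experimental | Mean visits | Ratio rejects (SD 3.3 / 4.8 / 6.4) | Visits reject (same order) |
|---|---|---|---|
| 12 vs 15 | 9.0 vs 11.25 | 5.1% / 5.5% / 5.3% | 92.3% / 74.2% / 52.1% |
| 12 vs 13.2 | 9.0 vs 9.9 | 5.5% / 5.0% / 4.9% | 28.7% / 18.4% / 13.9% |

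The ratio stays near 5% by construction, since attendance is equal in both arms. With equal schedules, all rejection rates are 4.8–5.2%.

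*(b) Dropout.* Weeks retained = min(geometric, 12), with one session per week and show rate s = 0.60, 0.75 or 0.90. The ratio is visits / (weeks + min(k, 12 − weeks)), where k is the number of post-dropout no-shows counted. Mean weeks retained = (1 − (1 − d)¹²)/d, with d the weekly dropout: 6.5 at 12%, 7.5 at 9% and 8.7 at 6%.

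| Weekly dropout, control vs experimental | Ratio, k = 0 | Ratio, k = 1 | Ratio, all counted (= visits) | Weeks retained |
|---|---|---|---|---|
| 12% vs 6% | 6.3–6.8% | 24.8–58.4% | 74.9–83.5% | 85.2–85.7% |
| 12% vs 9% | 5.2–5.5% | 8.8–16.6% | 21.3–26.0% | 26.7–27.4% |

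Ranges run over the three show rates. With no effect (12% in both arms), all rejection rates are 4.6–5.3%.

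**The case against.** The strongest reply separates visits from retention. Visits are the numerator of Hypothesis 2, and the chart review and the cost sum ("Costs per individual were summed and averaged for t-test comparison between experimental and control groups") also touch on service volume, so the Conclusion's remark on amount of service has indirect results behind it. Dividing by scheduled sessions is also defensible at four facilities, because it removes differences in programme intensity unrelated to the intervention. The case that the intervention changes scheduling is thin: it rests on counselors saying that the recommendations were easy to build into treatment plans and would inform future planning. No passage says schedules differed, and costs did not differ significantly. The simulations use assumed inputs, and in (b) counting two post-dropout no-shows already lifts the ratio to about 48–74% at 12% versus 6%. The no-show rule may be in the protocol, which is not at hand. Finally, it is literally true that an impact was not demonstrated if it was never tested.

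Much of this limits the size of the claim, and it is accepted to that extent. The simulations do not estimate an effect in this trial, and the missing no-show rule on its own is a request for clarification. Visits could also have been counted per interval, although contrasts against baseline would still fit poorly. The gap itself remains. A percentage, an attendance ratio and a price-weighted sum are not a visit count, and nothing at all addresses time in treatment. The SAP never says that engagement replaces the two questions. Placed beside tested outcomes, the word retention reads as a tested null.

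**Conclusion.** The concern holds and should be corrected. Two of three primary questions have no direct endpoint and no result, and the Conclusion's mention of retention rests on no retention analysis. This follows from the text alone. That the ratio is blind to scheduled volume is arithmetic. Its sensitivity to dropout cannot be settled without the no-show rule.

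The consequence for this trial cannot be sized. The simulations show only that a null Hypothesis 2 is compatible with sizeable differences in visits or retention. They also show that direct endpoints would often miss modest effects (14–29% rejection for visits with 10% more sessions scheduled; 21–27% for visits or weeks at 12% versus 9% dropout). Counselor clustering would lower these figures further.

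**What to change.** 1. Compare sessions attended per client as a count over the study period, for example by negative binomial regression. Use an offset for observation time if the period varies between clients, and account for counselor clustering. Facility adjustment is a sensible addition, since programme intensity may differ by site. Report the estimate with a confidence interval and label it post hoc.
2. If the charts hold last-session dates, analyse time from baseline to last attended session, censoring clients still attending, with the same clustering and labelling. If they do not, state that retention was not analysed and remove it from the Conclusion.
3. Describe Hypothesis 2 as attendance at scheduled sessions and give mean attended and mean scheduled sessions by arm. State the rule for sessions after the last attended one, and do not offer the ratio as evidence on retention.
4. In the Primary Analytic Approach, confine the condition-by-time model to outcomes with baseline and follow-up values, that is, the ASI-MV scores.

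The minimum cost is rewording in three places plus two means per arm. Item 1 needs no new data, because the count is already the numerator of Hypothesis 2. Item 2 depends on dates that the document does not confirm. The drawbacks are that the added analyses are post hoc with low power for modest effects, and that the Conclusion becomes narrower.

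### The t-tests for Primary Hypotheses 2, 3 and 5 drop the counselor effect without a stated reason, and the text is unclear on whether counselors or clients were assigned

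*SAP*

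**What the plan says.** Under Primary Analytic Approach, the SAP lists access to services, treatment visits and retention as the main questions, with psychosocial outcomes and drug use as secondary ones. It then selects a mixed model, in part to "take into account nesting of clients within counselors", and specifies: "Each mixed model will include fixed effects (condition, time and condition-by-time); random effects (clients nested within counselors".

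Under Analyses by Hypothesis, three comparisons are made differently:

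- **Hypothesis 2**, attended sessions over scheduled sessions: "An independent samples T-test was utilized to determine whether there were statistically significant differences between participants in the experimental and control groups".
- **Hypothesis 3**, number of relapses: an independent-samples t-test "was conducted to evaluate whether participants number of relapses differed significantly between the experimental and control groups".
- **Hypothesis 5**, cost: "Costs per individual were summed and averaged for t-test comparison between experimental and control groups".

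Only Hypothesis 4 (the ASI-MV composites) names a mixed model.

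On assignment, Results (Client Participants) says: "Forty-seven participants were randomized into the control, TAU, condition and 93 were randomized into the experimental condition". Hypothesis 6, however, is worded "Counselors in the experimental condition will report satisfaction with the BH-CDS Program", and formal testing is waived there "Due to the small number of counselors in the experimental and control groups". The Hypothesis 6 results then describe those counselors who had seen the recommendations.

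**The concern.** The document sets out an approach that allows for clients sharing a counselor, then analyses three outcomes as if all clients were independent, without explanation. Two of the three, engagement and relapses, correspond closely to outcomes named in the general approach (visits and retention, and drug use).

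The general model is longitudinal, so it cannot be applied as written to one ratio or total per client. That removes the time and condition-by-time terms. It does not remove the counselor term, since a counselor random intercept can be fitted to a single measure per client. No such reduced form is given.

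The consequence turns on who was assigned. If each counselor belonged to one arm, any positive correlation among a counselor's clients makes the t-test's standard error too small. If counselors had clients in both arms, it does not. The Conclusion reports no demonstrable effect on outcome, retention, services or cost, so the precision behind those nulls is what is at stake.

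**Working it through.** **Inputs from the SAP (Results).** 24 counselors at four facilities; 140 clients; 47 control and 93 experimental (47 + 93 = 140). Mean caseload is 140/24 = 5.83. The document gives no power, effect size, SD or ICC, so there is no design figure to reproduce.

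**Assumptions.** Two-sided 5% level; ICC 0, 0.05, 0.10 or 0.15; near-equal caseloads; normal outcomes; and, for power, a difference of 0.505 SD, chosen because it gives 80% power at 47 vs 93 under independence.

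**Case A: counselors assigned to arms.**

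- Design effect: DE = 1 + (5.83 − 1) × ICC. At ICC 0.10 this is 1 + 4.83 × 0.10 = 1.48.
- True level of the t-test: 2[1 − Φ(1.96/√DE)]. At ICC 0.10: 2[1 − Φ(1.96/1.218)] = 10.8%.
- Half-width of the 95% interval in SD units: t(0.975, df) × √[DE × (1/47 + 1/93)]. The t-test assumes DE = 1 and 138 df: 1.977 × 0.179 = 0.354. With clustering at ICC 0.10 and 22 df (24 counselors less 2): 2.074 × 0.179 × 1.218 = 0.452.
- Power: noncentral t at 0.505 SD with 22 df.

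| ICC | DE | t-test level, formula | t-test level, simulated | Half-width, 22 df | Power, 22 df | Random-intercept level, simulated |
|---|---|---|---|---|---|---|
| 0 | 1.00 | 5.0% | about 5% | 0.37 | 77% | 3.5–3.7% |
| 0.05 | 1.24 | 7.9% | about 8% | 0.41 | 68% | 4.0–4.2% |
| 0.10 | 1.48 | 10.8% | 10–11% | 0.45 | 60% | 4.7–4.9% |
| 0.15 | 1.725 | 13.6% | 12–14% | 0.49 | 54% | 4.9% |

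The t-test's own figures, assuming independence on 138 df, are a half-width of 0.35 and power of 80%. The simulations used 12 + 12 or 8 + 16 counselors, with 10,000 to 20,000 trials per t-test scenario and 10,000 per random-intercept scenario (REML, 22 df). Unequal caseloads make matters worse: with an assumed coefficient of variation of 0.6, the formula level rises to 9.1% at ICC 0.05 and 13.2% at ICC 0.10.

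**Case B: clients balanced between arms within counselor.** At ICC 0 / 0.05 / 0.10 / 0.15, the simulated t-test level is 4.8% / 4.6% / 3.9% / 3.3%. The random-intercept model (115 df) holds 5.2% / 5.1% / 5.1% / 4.8%. Its power is 80% / 82% / 83% / 85%, against 80% / 80% / 81% / 82% for the t-test.

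**Case C: clients randomized without regard to counselor.** The simulated t-test level is about 5% throughout.

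**The case against.** The strongest reply has four parts.

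- **Scope.** The general section describes a repeated-measures model, and the only outcome stated to be measured at baseline, one month and three months is the ASI-MV, which does get one. The SAP says what each mixed model contains, not that every hypothesis has one. This stands in part: it explains the missing time terms, but not the missing counselor term, because the approach was introduced for visits, retention and drug use as well. Cost is not on that list, so Hypothesis 5 is not a departure from the general section; it merely shares the weakness.
- **Assignment.** The most direct statement is that participants were randomized, and on that reading the t-test keeps its level or is slightly conservative. The contrary evidence is indirect, and the reference to counselors who saw the recommendations fits either design. This stands: inflation is possible, not shown. But if every counselor had clients in both arms, counselors would not fall into experimental and control groups, so the ambiguity is real.
- **Consequence.** All three results are null, and correcting for counselor assignment would not be expected to make them positive. This stands, and it confines the effect to how the nulls are read.
- **Size.** The ICCs are assumed, and some of the loss in Case A comes from degrees of freedom. At ICC 0, moving from 138 to 22 df alone lowers power from 80% to 76.9% and widens the half-width from 0.354 to 0.371. This also stands; the remainder is due to clustering.

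**Conclusion.** The concern holds and should be fixed. Hypotheses 2 and 3 depart from the SAP's own reason for choosing a mixed model, without explanation, and Hypothesis 5 has the same gap. The size is conditional. Under counselor assignment with an ICC of 0.05 to 0.15, the nominal 5% test runs at about 8% to 14%, and the appropriate intervals are roughly 17% to 38% wider than the t-test's (0.414/0.354 = 1.17; 0.487/0.354 = 1.38). Under balance within counselor, the cost is at most about 3 points of power. Under unrestricted client randomization, the level is unaffected.

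None of the three tests was significant, so no false positive arose. What needs correcting is the precision attributed to the null results. Confidence is medium, because the ICC, the caseload distribution and the unit of assignment are not settled by the document.

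**What to change.** 1. State the unit of assignment (counselor, or client within counselor) and reconcile the Hypothesis 6 wording with the Results.
2. Re-analyse Hypotheses 2, 3 and 5 with the general model reduced to a single measure: a fixed condition effect and a counselor random intercept, with small-sample degrees of freedom for 24 counselors. Cluster-robust standard errors with a small-sample correction would also serve. Otherwise, state why the counselor term was omitted.
3. Report each between-group difference with its 95% interval and the estimated counselor ICC.

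Facility effects and count models are optional.

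The cost is some SAP wording and a re-run of three comparisons; the only added input is which counselor treated each client. If counselors were assigned, intervals widen and degrees of freedom fall from 138 to about 22. With an ICC near zero, the random-intercept model on 22 df is then slightly conservative (simulated level about 3.5%).

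### Hypotheses 2, 3 and 5 are tested by plain t-tests that drop both the covariate adjustment and the counselor nesting for which the SAP chose a mixed model

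*SAP*

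**What the plan says.** The Primary Analytic Approach gives its reasons for the method: "A mixed model analytic approach was chosen for its ability to: adjust for individual-level covariates; take into account nesting of clients within counselors". The covariates it has in mind are described as potential and demographic, with counselor experience and client age as the named cases. It adds: "Non-significant covariates will be removed systematically".

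Under Analyses by Hypothesis the methods differ:

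- Primary Hypothesis 2 (share of scheduled sessions attended): "An independent samples T-test was utilized to determine whether there were statistically significant differences".
- Primary Hypothesis 3 (number of relapses): an independent-samples t-test "was conducted to evaluate whether participants number of relapses differed significantly between the experimental and control groups".
- Primary Hypothesis 5 (cost of services): "Costs per individual were summed and averaged for t-test comparison between experimental and control groups".
- Primary Hypothesis 4 (the seven ASI-MV composites) is the only one given a mixed model. Its section also states: "The ASI-MV was administered at baseline, 1-month follow-up and 3-month follow-up".

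None of the three t-test sections mentions a covariate or a counselor effect, or explains the change of method. The Results section reports 47 control and 93 experimental clients and 24 counselors. It describes all three comparisons as not significant, with no estimate or interval.

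**The concern.** The SAP gives two reasons for modelling rather than comparing raw means, and then compares raw means on three of its hypotheses. Both omissions matter.

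First, variation in attendance, relapse and cost that age or baseline severity could explain stays in the error term. All three results are null, and the Conclusion relies on them, so lost precision would make those nulls less informative.

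Second, a two-sample t-test treats all 140 clients as independent. If clients of one counselor resemble each other, its standard error may be wrong, and covariate adjustment alone would not repair that.

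**Working it through.** The SAP gives no power calculation, significance level, SD or covariate-outcome correlation, so there is no stated figure to reproduce. The arithmetic below is illustrative.

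**Inputs from the SAP (Results):** 47 and 93 clients, 140 in total; 24 counselors.
**Assumptions:** two-sided 5%, 80% power, independent clients, and a multiple correlation r of 0.1 to 0.5 between the baseline covariates and the outcome within arm.

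**1. Unadjusted detectable difference**, in SD units:
(1.960 + 0.842) × √(1/47 + 1/93) = 2.802 × 0.1790 = 0.501 SD.

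**2. Adjusted.** Residual variance is multiplied by 1 − r², so the detectable difference is multiplied by √(1 − r²). The equivalent unadjusted sample is 140/(1 − r²). Power is for a true difference of 0.501 SD.

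| Assumed r | 1 − r² | Detectable difference (SD) | Power | Equivalent N |
|---|---|---|---|---|
| 0.1 | 0.99 | 0.499 | 80.4% | 141 |
| 0.2 | 0.96 | 0.491 | 81.6% | 146 |
| 0.3 | 0.91 | 0.478 | 83.6% | 154 |
| 0.4 | 0.84 | 0.460 | 86.4% | 167 |
| 0.5 | 0.75 | 0.434 | 89.9% | 187 |

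**3. Charge for estimating the covariates.** With k covariates the variance factor becomes (1 − r²) × 137/(137 − k), where 137 = 140 − 3.

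- r = 0.1: 0.99 × 137/134 = 1.012 for k = 3, and 0.99 × 137/133 = 1.020 for k = 4. This is a slight loss.
- r = 0.3: 0.930 and 0.937, so 0.501 × √0.930 = 0.484 SD and 0.501 × √0.937 = 0.485 SD.
- r = 0.5: 0.767 and 0.773, giving 0.439 and 0.441 SD.
- Break-even is at r² = k/137, which is r = √(3/137) = 0.15 for three covariates and √(4/137) = 0.17 for four.

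**4. Counselor nesting.** Average clients per counselor: 140/24 = 5.83. If whole counselors were assigned to an arm, the design effect is 1 + (5.83 − 1) × ICC, taking equal caseloads. An assumed ICC of 0.01 gives 1.048 and 0.10 gives 1.483. The true error rate of a nominal 5% t-test is 2 × [1 − Φ(1.96/√design effect)], which is 5.6% and 10.8% respectively. The SAP does not clearly state the unit of allocation. The Client Participants paragraph speaks of participants being randomized, while Primary Hypothesis 6 treats counselors as belonging to arms. The design-effect figures apply only to the second case.

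**The case against.** The strongest reply is that the general section is written for repeated measures. Its covariates belong to a model with time and condition-by-time terms. Attendance ratio, relapse count and summed cost are each one value per client, so that model cannot be fitted to them as written; the outcome measured at three time points does receive it. This stands as to the time terms. It does not explain losing the other two features, since a regression on one value per client can carry both covariates and a counselor effect.

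A reader might infer that the SAP promised adjustment and broke the promise. The text does not support that. The covariates are only potential, non-significant ones are to be removed, and an unadjusted final model was therefore allowed. The baseline ASI-MV composites are never named as covariates; using them is this review's proposal. That they predict relapse, attendance or cost is plausible but not shown in the document.

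It is also fair to say that an unadjusted comparison of individually randomized clients is valid, with chance imbalance already reflected in its standard error. The SAP calls demographics broadly alike and says nothing about baseline severity, so no severity imbalance is shown.

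Finally, although all three are headed as primary hypotheses, the opening section lists drug use as secondary and does not list cost. Calling them three main outcomes would go too far.

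**Conclusion.** The point holds as an unexplained departure from the SAP's own analytic approach, with a possible cost in precision and an open question about clustering. If clients were randomized individually, the missing covariates do not bias the result. The gain from adjusting runs from about nil (r = 0.1) through modest (r = 0.3, 0.50 to 0.48 SD) to material (r = 0.5, 0.50 to 0.43 SD, or 0.44 SD after the charge for estimating covariates). All of this assumes independent clients, two-sided 5% and 80% power.

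Two stronger conclusions are tempting. One is that precision was demonstrably thrown away; without a correlation or SD in the document, that cannot be shown. The other is that adjustment would overturn the null findings; no estimate or interval is reported, so nothing can be said about that.

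The statement about bias has a limit. The SAP does not say whether the 190 − 140 = 50 clients who were not fully enrolled left before or after allocation. The inflated error rates in the working depend on allocation by counselor, which is not established.

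**What to change.** Reconcile the Primary Analytic Approach with the sections on Hypotheses 2, 3 and 5. For these three, replace the t-test with a regression of the per-client outcome on:

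- condition;
- a counselor random effect;
- a short list of baseline covariates kept regardless of significance: age and the baseline ASI-MV drug and alcohol composites, plus the psychiatric composite for Hypotheses 2 and 5.

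Report the adjusted arm difference with its 95% interval. State the unit of allocation, since it decides how much the counselor term matters.

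The data are already held. The covariates use three degrees of freedom for Hypothesis 3 and four for Hypotheses 2 and 5, out of 140 − 2 = 138. If counselors turn out to have been allocated, the arm comparison rests on about 24 − 2 = 22 counselor-level degrees of freedom, and intervals may widen. Because results are already reported, the list can no longer be called prespecified: label the re-analysis post hoc and show it beside the reported t-tests.
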